## 12.2.5. Safety

For a given subject and the analysis of solicited symptoms within 7 days post-vaccination, missing or non-evaluable measurements will not be replaced. Therefore, the analysis of the solicited symptoms based on the ES will include only vaccinated subjects for doses with documented safety data (i.e., symptom screen completed). More specifically the following rules will be used:

- Subjects who documented the absence of a solicited symptom after one dose will be considered not having that symptom after that dose.
- Subjects who documented the presence of a solicited symptom and fully or partially recorded daily measurement over the solicited period will be included in the summaries at that dose and classified according to their maximum observed daily recording over the solicited period. ***The missing recorded daily measurements will be assigned to the lowest intensity category (i.e. grade 1).***
- Subjects who documented the presence of a solicited symptom after one dose without having recorded any daily measurement will be assigned to the lowest intensity category at that dose (i.e., grade 1).
- Doses without symptom sheets documented will be excluded.

For analysis of unsolicited AEs, such as SAEs or AEs by primary MedDRA term, all vaccinated subjects will be considered. Subjects who did not report an event will be considered as subjects without an event.

Note that for all tables described in this section, the way the percentage of subjects will be derived will depend on the event analyzed (see table below for details). As a result, the N value will differ from one table to another.

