## 1. DOCUMENT HISTORY

Date	Description	Protocol Version
26 JAN 2018	First version	Amendment 1 – 24 October 2017
18 JUL 2018	Amendment 1: The following changes were made: - Alignment with Protocol Amendment 2 (in bold italic) - Corrections (in bold italic) - Update of templates	Amendment 2 – 16 March 2018
11 FEB 2019	Amendment 2: The following changes were made: - Alignment with Protocol Amendment 3 (in bold italic) - Corrections (in bold italic) - Update of templates	Amendment 3 - 07 December 2018
12 SEP 2019	Amendment 3: The following changes were made: - Alignment with Protocol Amendment 4 (in bold italic and by deleting) - Addition of Section 10 (new SAP template) - Change in Sections 11 and 12.2.5 (in bold italic)	Amendment 4 - 11 July 2019

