**Table 7 FDA toxicity grading scales for hematology/biochemistry parameters**

Serum*	Mild (Grade 1)	Moderate (Grade 2)	Severe (Grade 3)	Potentially Life Threatening (Grade 4)**
Blood Urea Nitrogen - BUN	23 – 26	27 – 31	> 31	Requires dialysis
Creatinine – mg/dL	1.5 – 1.7	1.8 – 2.0	2.1 – 2.5	> 2.5 or requires dialysis
Liver Function Tests –ALT, AST increase by factor	1.1 – 2.5 x ULN	2.6 – 5.0 x ULN	5.1 – 10 x ULN	> 10 x ULN

ULN = upper limit of the normal range.

\*The laboratory values provided in the tables serve as guidelines and are dependent upon institutional normal parameters. Institutional normal reference ranges should be provided to demonstrate that they are appropriate.

\*\*The clinical signs or symptoms associated with laboratory abnormalities might result in characterization of the laboratory abnormalities as Potentially Life Threatening (Grade 4). For example, a low sodium value that falls within a Grade 3 parameter (125-129 mE/L) should be recorded as a Grade 4 hyponatremia event if the subject had a new seizure associated with the low sodium value.

Hematology*	Mild (Grade 1)	Moderate (Grade 2)	Severe (Grade 3)	Potentially Life Threatening (Grade 4)
Hemoglobin (Female) - gm/dL	11.0 – 12.0	9.5 – 10.9	8.0 – 9.4	< 8.0
Hemoglobin (Female) change from baseline value - gm/dL	Any decrease – 1.5	1.6 – 2.0	2.1 – 5.0	> 5.0
Hemoglobin (Male) - gm/dL	12.5 – 13.5	10.5 – 12.4	8.5 – 10.4	< 8.5
Hemoglobin (Male) change from baseline value - gm/dL	Any decrease – 1.5	1.6 – 2.0	2.1 – 5.0	> 5.0
WBC Increase - cell/mm 	10 800 – 15 000	15 001 – 20 000	20 001 – 25 000	> 25 000
WBC Decrease - cell/mm 	2 500 – 3 500	1 500 – 2 499	1 000 – 1 499	< 1 000
Lymphocytes Decrease - cell/mm 	750 – 1 000	500 – 749	250 – 499	< 250
Neutrophils Decrease - cell/mm 	1 500 – 2 000	1 000 – 1 499	500 – 999	< 500
Eosinophils - cell/mm 	650 – 1 500	1 501 – 5 000	> 5 000	Hyper-eosinophilic
Platelets Decreased - cell/mm 	125 000 – 140 000	100 000 – 124 000	25 000 – 99 000	< 25 000

\*The laboratory values provided in the tables serve as guidelines and are dependent upon institutional normal parameters. Institutional normal reference ranges should be provided to demonstrate that they are appropriate

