**Template 14 Compliance in completing solicited symptoms information <Cohort name>**

DOSE	Symptom information	<Each group>		<Each group>		
		N	n	Compliance (%)	N	n
DOSE <each dose number>	General SS	xxx	xxx	xx.x	xxx	xxx
	Local SS	xxx	xxx	xx.x	xxx	xxx
TOTAL	General SS	xxx	xxx	xx.x	xxx	xxx
	Local SS	xxx	xxx	xx.x	xxx	xxx

Short group label = long group label

N = Number of administered doses

n = number of doses with SS returned

General SS = Symptom screens used for the collection of general solicited AEs

Local SS = Symptom screens used for the collection of local solicited AEs

Compliance (%) = (n / N) X 100

**Template 15 Incidence and nature of <grade 3> adverse events (solicited and unsolicited) <with causal relationship to vaccination> reported during the 7-day (Days 1-7) post-vaccination period following each dose and overall <Cohort name>**

		<Each group>					<Each group>				
					95% CI					95% CI	
Dose	Symptoms	N	n	%	LL	UL	N	n	%	LL	UL
DOSE 1	Any symptom	XXX	XXX	XX.X	XX.X	XX.X	XXX	XXX	XX.X	XX.X	XX.X
	General symptoms	XXX	XXX	XX.X	XX.X	XX.X	XXX	XXX	XX.X	XX.X	XX.X
	Local symptoms	XXX	XXX	XX.X	XX.X	XX.X	XXX	XXX	XX.X	XX.X	XX.X
DOSE 2	Any symptom	XXX	XXX	XX.X	XX.X	XX.X	XXX	XXX	XX.X	XX.X	XX.X
	General symptoms	XXX	XXX	XX.X	XX.X	XX.X	XXX	XXX	XX.X	XX.X	XX.X
	Local symptoms	XXX	XXX	XX.X	XX.X	XX.X	XXX	XXX	XX.X	XX.X	XX.X
OVERALL/DOSE	Any symptom	XXX	XXX	XX.X	XX.X	XX.X	XXX	XXX	XX.X	XX.X	XX.X
SUBJECT	General symptoms	XXX	XXX	XX.X	XX.X	XX.X	XXX	XXX	XX.X	XX.X	XX.X
	Local symptoms	XXX	XXX	XX.X	XX.X	XX.X	XXX	XXX	XX.X	XX.X	XX.X

Short group label = long group label

For each dose:

N = number of subjects with the corresponding administered dose

n/% = number/percentage of subjects presenting at least one type of symptom following the corresponding dose

For overall/dose:

N = number of administered dose

n/% = number/percentage of doses followed by at least one type of symptom

For overall/subject:

N = number of subjects with at least one administered dose

n/% = number/percentage of subjects presenting at least one type of symptom

95% CI = Exact 95% confidence interval; LL = lower limit, UL = upper limit

**Template 16 Incidence of solicited local symptoms reported during the 7-day  
(Days 1-7) post-vaccination period following each dose and overall  
<Cohort name>**

Dose	Symptom	Type	<Each Group>			
			95% CI			
N	n	%	LL	UL		
DOSE x	<Each local symptom>	ALL GRADE $\geq 2$ GRADE 3 MEDICAL ADVICE ALL GRADE $\geq 2$ GRADE 3 MEDICAL ADVICE				

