**Template 24 Incidence of concomitant medication during the study period by dose and overall <Cohort name>**

Dose		<Each group>						<Each group>					
		<95>% CI			<95>% CI			<95>% CI			<95>% CI		
		N	n	%	LL	UL		N	n	%	LL	UL	
DOSE x	Any	xx	xx	xx.x	xx.x	xx.x	xx	xx	xx	xx.x	xx.x	xx.x	
	Antipyretics												
	Prophylactic antipyretics	xx	xx	xx.x	xx.x	xx.x	xx	xx	xx	xx.x	xx.x	xx.x	
OVERALL/DOSE	Any	xx	xx	xx.x	xx.x	xx.x	xx	xx	xx	xx.x	xx.x	xx.x	
	Antipyretics												
	Prophylactic antipyretics	xx	xx	xx.x	xx.x	xx.x	xx	xx	xx	xx.x	xx.x	xx.x	
OVERALL/SUBJECT	Any	xx	xx	xx.x	xx.x	xx.x	xx	xx	xx	xx.x	xx.x	xx.x	
	Antipyretics												
	Prophylactic antipyretics	xx	xx	xx.x	xx.x	xx.x	xx	xx	xx	xx.x	xx.x	xx.x	

Short group label = long group label

For each dose:

N = total number of subjects with the corresponding administered dose

n/% = number/percentage of subjects who started the specified type of concomitant medication at least once during the considered period

For overall/dose:

N = number of administered doses

n/% = number/percentage of doses after which the specified type of concomitant medication was started at least once during the considered period

For overall/subject:

N = total number of subjects with at least one administered dose

n/% = number/percentage of subjects who started the specified type of concomitant medication at least once during the considered period

95% CI = Exact 95% confidence interval; LL = lower limit, UL = upper limit

**Template 25 Summary of hematology and biochemistry results by maximum grade from VISIT x (Dx) up to VISIT y (Dy) versus baseline <Cohort name>**

Laboratory parameter	Baseline (PRE)	VISIT x (Dx) up to VISIT y (Dy)	<Each group>			<Each group>		
			N	n	%	N	n	%
*	Grade 0	Grade 0						
		Grade 1						
		Grade 2						
		Grade 3						
	Grade 1	Grade 0						
		Grade 1						
		Grade 2						
		Grade 3						
	Grade 2	Grade 0						
		Grade 1						
		Grade 2						
		Grade 3						
	Grade 3	Grade 0						
		Grade 1						
		Grade 2						
		Grade 3						
	Total	Grade 0						
		Grade 1						
		Grade 2						
		Grade 3						

Short group label = long group label

N = number of subjects with at least one available result for the specified laboratory parameter and follow-up period

n/% = number/percentage of subjects reporting at least once the laboratory event when the maximum grading over the follow-up period is considered

\*Applicable laboratory parameters:

[figure not shown]

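### SAP 12.2.5 counts blank diary days of a declared symptom as grade 1 while also saying missing values are not replaced; separately, Templates 25 and 26 have no Grade 4 row

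*SAP*

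**What the plan says.** **Diary data.** Section 12.2.5 of the current SAP (Amendment 3) opens the rules for solicited symptoms with the statement that "missing or non-evaluable measurements will not be replaced". Bulleted rules follow. The second bullet covers "Subjects who documented the presence of a solicited symptom and fully or partially recorded daily measurement over the solicited period"; these subjects are to be "classified according to their maximum observed daily recording over the solicited period". The same bullet then ends: "The missing recorded daily measurements will be assigned to the lowest intensity category (i.e. grade 1". The document history records this revision as "Change in Sections 11 and 12.2.5 (in bold italic", and the corresponding bullet in SAP Amendment 2 (section 11.2.5) lacks the closing sentence. The third bullet, present since the first SAP version, gives grade 1 to a dose for which the symptom was declared but no daily value was recorded.

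Section 6.3.2 plans a summary of the number of days with each symptom, by dose; the shell is Template 18.

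**Laboratory data.** Table 7 has a fourth severity column, "Potentially Life Threatening (Grade 4", and section 6.3.1 tabulates laboratory values by toxicity grade without setting an upper limit. Template 25, "Summary of hematology and biochemistry results by maximum grade from VISIT x (Dx) up to VISIT y (Dy) versus baseline", lists Grades 0 to 3 only, both at baseline and afterwards. Template 26, for the maximum hemoglobin change, also stops at Grade 3.

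**The concern.** Two opposite missing-data rules apply to the same blank day. One leaves it missing and grades on what was observed; the other fills it with a symptom. A programmer who follows the added sentence will count every blank day of a declared symptom as a day with that symptom. Reported duration then depends partly on how fully diaries were completed.

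Grade 1 is also not the bottom of the SAP's daily scales. Table 5 starts at grade 0 for pain and for the general symptoms other than fever, and Table 6 gives grade 0 to redness or swelling up to 20 mm. For temperature, grade 1 means 38 to 38.5°C, so a blank temperature day would be treated as a fever day.

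Solicited events and laboratory abnormalities are primary safety endpoints (section 4.1). The number of symptom days is an additional summary of the former. For the laboratory data, the stake is that the most severe category has no place in the two tables meant to show the worst grade reached.

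**Working it through.** The SAP states no figure for this point, so there is none to reproduce. The checks below are of the rule's logic and of its size under assumed inputs.

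**1. Can the imputation change a subject's maximum grade?** Take every 7-day diary in which each day is grade 0, 1, 2, 3 or blank, with at least one recorded and at least one blank day.

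- Number of such patterns: 5^7 − 4^7 − 1 = 78,125 − 16,384 − 1 = 61,740.
- Replacing blanks by grade 1 changes the maximum only if every recorded day is grade 0: 2^7 − 2 = 126 patterns.

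This counts patterns, not how often they occur. An observed maximum of 1, 2 or 3 never changes. The 126 patterns become grade 1 only if imputed days are allowed to count as observed, which the text does not settle.

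**2. Effect on symptom days (Template 18).** Let d be the true number of symptom days out of 7 and m the share of days left blank at random. The symptom is declared present and at least some days are recorded. The SAP gives neither d nor m; all values below are assumptions.

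- Recorded days only: d(1 − m). Error against truth: −dm.
- Blank counted as grade 1: d(1 − m) + 7m. Error against truth: +(7 − d)m.

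For d = 2.5:

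| m | Recorded only | Error | Blank = grade 1 | Error |
|---|---|---|---|---|
| 2% | 2.45 | −0.05 (−2%) | 2.59 | +0.09 (+4%) |
| 5% | 2.375 | −0.125 (−5%) | 2.725 | +0.225 (+9%) |
| 10% | 2.25 | −0.25 (−10%) | 2.95 | +0.45 (+18%) |

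Over a wider range:

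| d | m | Recorded only | Blank = grade 1 | Blank = grade 1, relative to truth |
|---|---|---|---|---|
| 1 | 5% | 0.95 | 1.30 | 1.30 |
| 1 | 20% | 0.80 | 2.20 | 2.20 |
| 2 | 10% | 1.80 | 2.50 | 1.25 |
| 3 | 5% | 2.85 | 3.20 | 1.07 |
| 3 | 20% | 2.40 | 3.80 | 1.27 |

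Short symptoms are inflated most, so contrasts shrink. At m = 10%, a true threefold difference (3 days against 1) appears as 3.4/1.6 = 2.1 with imputation, and as 2.7/0.9 = 3.0 on recorded days.

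**3. Laboratory shells.** No arithmetic applies. Table 7 assigns Grade 4 to, for example, creatinine above 2.5 mg/dL, ALT or AST above 10 times the upper limit of normal, and platelets below 25,000. Section 6.3.1 does not cap the grading. Templates 25 and 26 offer four rows, Grades 0 to 3. Programmed as drawn, a Grade 4 value must either be left out or be placed under Grade 3.

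**The case against.** **The no-replacement statement may be a general principle with exceptions.** Section 12.2.5 draws from it that only doses with documented data are included, and then announces more specific rules. On that reading it concerns whole missing doses, and the bullets govern the detail. This softens the conflict but does not remove it: the same bullet that imputes grade 1 also classifies by what was observed, and nothing says which outputs the imputation serves.

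**Counting blanks as symptomatic is conservative for safety.** This stands in part. Recorded days only is biased downwards, by d × m, so neither rule is unbiased. That supports keeping the imputed count as a sensitivity analysis, not an unexplained sentence that conflicts with its surroundings.

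**The shells are only illustrations.** The introduction to Annex 2 says displays will be adapted to the study. This stands: the Grade 4 gap is one of display, not of grading. Even so, the omission runs through all four SAP versions supplied.

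Two stronger readings are tempting and not supported:

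- A reader might infer that the safety rules misgrade subjects at both ends. They do not. The imputation requires a declared symptom and cannot alter an observed maximum of grade 1 or more, and Table 7 defines Grade 4 properly.
- A reader might infer that Template 15 contradicts 12.2.5, because its denominator is "N = number of subjects with the corresponding administered dose" while doses without a symptom sheet are to be excluded. But Template 15 combines solicited and unsolicited events, and Table 4 sets the unsolicited denominator to all vaccinated subjects. Section 12.2.5 warns that N differs between tables, and the purely solicited Templates 16 and 17 already use documented doses.

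**Conclusion.** The concern holds in a limited form. The sentence added in Amendment 3 conflicts with the no-replacement rule and with classification by observed values, and if followed it lengthens reported symptom duration. With an assumed true duration of 2.5 days and 2% to 10% of days blank at random, the excess is 0.09 to 0.45 day. Over the wider assumed range (1 to 3 days, 5% to 20% blank) the reported mean is 1.07 to 2.2 times the truth. The real size depends on diary completeness, which the SAP does not give. Maximum grade is at risk only for a declared symptom with a partial diary of grade 0 values, and only if imputed days count as observed.

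Separately, the maximum-grade laboratory shells omit a level that the SAP itself defines. Such results are probably rare, but the tables as drawn have nowhere to put them.

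**What to change.** 1. Delete the added sentence in 12.2.5, and state that both maximum grade and number of symptom days use recorded days only. The third bullet, on declared symptoms with no daily values, can stay.
2. Add a sensitivity version of Template 18 in which every blank day of a declared symptom counts as symptomatic. Recorded-only and blank-as-symptomatic are the lower and upper limits of each subject's count, so the pair brackets the truth whatever caused the blanks.
3. Add a Grade 4 level to Template 25 (baseline, post-baseline and total) and to Template 26.

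The cost is a wording change, one extra table and minor programming. Headline durations become shorter and slightly understated, by 2%, 5% or 10% at those blank rates; this should be noted beside the table. Annex 2 allows minor shell changes without an SAP amendment, so item 3 may need none.

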- **Enrolment:** the study will follow a staggered enrolment with 2 steps; the first being Phase I (N = ~80) and the second being Phase II (N = ~390):
  - Phase I: During the Phase I enrolment, subjects will be vaccinated one at a time, at least 60 minutes apart, with a maximum of 10 subjects/day until ~80 subjects are enrolled (i.e. to obtain treatment groups of at least 8 subjects/group). If no safety issue is identified by the Independent Data Monitoring Committee (IDMC) upon review of the 7-day post-dose 1 safety data (Days 1-7) of all Phase I subjects (N = ~80), Phase II enrolment will be allowed to start.
  - Phase II: Subjects will be enrolled and vaccinated without limitation on the number of vaccinees per day or time between consecutive subjects.
- **Vaccination schedule:**
  - Two primary doses at Visit 1 (Day 1) and Visit 4 (Day 57).
  - A booster dose at Visit 8 (Month 14).
- **Definition of the different epochs:**
  - Epoch 001: Screening (Day -28 to -2) – only for Phase I subjects.
  - Epoch 002: Primary starting at Visit 1 (Day 1) and ending at Visit 7 (Month 8).
  - Epoch 003: Booster starting at Visit 8 (Month 14) and ending at Visit 12 (Month 26).

- **Intervals between study visits**

Interval	Optimal length of interval	Allowed interval**
Screening to Visit 1*	2-28 days	
Visit 1 → Visit 2	7 days	7-9 days
Visit 1 → Visit 3	28 days	28-38 days
Visit 1 → Visit 4	56 days	56-66 days
Visit 4 → Visit 5	7 days	7-9 days
Visit 4 → Visit 6	28 days	28-38 days
Visit 4 → Visit 7	168 days	168-196 days
Visit 4 → Visit 8	336 days	336-364 days
Visit 8 → Visit 9	7 days	7-9 days
Visit 8 → Visit 10	28 days	28-38 days
Visit 8 → Visit 11	168 days	168-196 days
Visit 8 → Visit 12	336 days	336-364 days

\* Only applicable for Phase I subjects. Screening evaluations may be completed 2 to 28 days before Day 1. Site staff should allow sufficient time between the screening and Day 1 visits to receive and review screening safety laboratory test results. If a delay occurs such that the interval between screening and the Day 1 vaccination exceeds 28 days, a re-screening visit should be scheduled before Visit 1.

\*\* Visits out of the allowed interval can lead to elimination from the Per-Protocol set for immunogenicity analysis.

- **Sampling schedule:**

- Blood samples for safety assessment will be drawn from all subjects at all visits: Screening\*, Days 1, 8, 29, 57, 64, 85, Month 8, Month 14, Month 14 + 7 days, Month 14 + 28 days, Month 20 and Month 26.

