Passive surveillance will be carried out from Visit 1 (after Dose 1) until the end of the study (Visit 12). Subjects will be instructed to contact the investigator/study staff as soon as they experience ILI symptoms. During the entire study period, nasal and throat swabs will be collected as soon as possible (preferably within 24 hours, but not later than 7 days) after the onset of an ILI to test for influenza and/or other respiratory pathogens by RT-PCR *if deemed necessary, or stored for future research.*

All cases of ILI have also to be recorded as unsolicited adverse event (AE) or serious adverse event (SAE) in the electronic Case Report Form (eCRF).

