## 4. ENDPOINTS

### 4.1. Primary endpoints

#### Reactogenicity and safety

- Occurrence of solicited local and general AEs after each vaccination:
  - Occurrence of solicited local AEs during a 7-day follow-up period (i.e. on the day of vaccination and 6 subsequent days) after each vaccine dose, in all vaccine groups.
  - Occurrence of solicited general AEs during a 7-day follow-up period (i.e. on the day of vaccination and 6 subsequent days) after each vaccine dose, in all vaccine groups.
- Occurrence of unsolicited AEs after each vaccination:
  - Occurrence of unsolicited AEs during a 28-day follow-up period (i.e. on the day of vaccination and 27 subsequent days) after each vaccine dose, in all vaccine groups.
- Occurrence of hematological and biochemical laboratory abnormalities after each vaccination:
  - Any hematological (red blood cells, white blood cells and differential count, platelets count and hemoglobin level) or biochemical (alanine aminotransferase, aspartate aminotransferase, creatinine, blood urea nitrogen [BUN] and BUN-to-creatinine ratio) laboratory abnormality at each visit subsequent to Day 1, in all vaccine groups.
- Occurrence of medically attended events (MAEs), potential immune-mediated diseases (pIMDs) and SAEs:
  - Occurrence of MAEs, pIMDs and SAEs throughout the entire study period, in all vaccine groups.

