#### **6.3.1. Analysis of safety planned in the protocol**

- The percentage of subjects with at least one local AE (solicited and unsolicited), with at least one general AE (solicited and unsolicited) and with any AE during the solicited follow-up period will be tabulated with exact 95% CI. The same calculations will be performed for AEs rated as grade 3.
- The percentage of subjects reporting each individual solicited local and general AE during the solicited follow-up period will be tabulated with exact 95% CI. The same tabulation will be performed for grade 3 AEs and for AEs with causal relationship to vaccination.

- The verbatim reports of unsolicited AEs will be reviewed by a physician and the signs and AEs will be coded according to the Medical Dictionary for Regulatory Activities (MedDRA). The percentage of subjects with at least one report of unsolicited AE classified by the MedDRA and reported up to 28 days after vaccination will be tabulated with exact 95% CI. The same tabulation will be performed for grade 3 unsolicited AEs and for unsolicited AEs with causal relationship to vaccination.
- The percentage of subjects with Medically Attended Event(s) (MAE(s)) will be summarized by group with exact 95% CI.
- The percentage of subjects with episode(s) of ILI will be summarized by group with exact 95% CI.
- At each hematology/biochemistry sampling timepoint, by study group, individual hematological and biochemical values will be presented as number of subjects out of range (above and below normal range) and tabulated by toxicity grading (refer to Appendix C of the protocol). In addition, changes from baseline (median/interquartile range) will be presented.
- SAEs and pIMDs will be described in detail. Withdrawals due to (S)AEs will also be summarized.

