**Table 4      Eligibility for safety analyses**

Event	N used for deriving % per subject for Vaccination phase	N used for deriving % per dose for Vaccination phase
Solicited general symptom	All subjects with at least one solicited general symptom documented as either present or absent (i.e., symptom screen completed)	All study visits with study vaccine administered and with at least one solicited general symptom documented as either present or absent (i.e., symptom screen completed)
Solicited local symptom	All subjects with at least one solicited local symptom documented as either present or absent (i.e., symptom screen completed)	All study visits with study vaccine administered and with at least one solicited local symptom documented as either present or absent (i.e., symptom screen completed)
Unsolicited symptom	All subjects with study vaccine administered	All study visits with study vaccine administered

The intensity of the following solicited AEs will be assessed as described:

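### In the whole-study MAE, SAE and ILI percentages, subjects who withdraw without a reported event count as event-free to Month 26, so withdrawal biases these percentages downward.

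*SAP*

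**What the plan says.** The rule is in SAP Section 12.2.5: "For analysis of unsolicited AEs, such as SAEs or AEs by primary MedDRA term, all vaccinated subjects will be considered". The next sentence reads: "Subjects who did not report an event will be considered as subjects without an event". Table 4 in the same section gives the per-subject denominator for unsolicited symptoms as "All subjects with study vaccine administered", under a column headed for the vaccination phase. Template 28 carries the same kind of denominator (subjects with an administered dose) into the table of SAEs over the study period.

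The windows are long. Section 4.1 lists among the primary safety endpoints: "Occurrence of MAEs, pIMDs and SAEs throughout the entire study period, in all vaccine groups". Section 2 defines the last epoch as "Booster starting at Visit 8 (Month 14) and ending at Visit 12 (Month 26"). ILI surveillance runs from Dose 1 to Visit 12, and Section 2 brings ILI under the unsolicited-event rule: "All cases of ILI have also to be recorded as unsolicited adverse event (AE) or serious adverse event (SAE").

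The planned summaries in Section 6.3.1 are proportions of subjects. For MAEs: "The percentage of subjects with Medically Attended Event(s) (MAE(s)) will be summarized by group with exact 95% CI". For ILI: "The percentage of subjects with episode(s) of ILI will be summarized by group with exact 95% CI". The current SAP (Amendment 3) has no person-time rate, time-to-event summary or completer denominator for these events.

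**The concern.** The rule turns non-observation into a negative outcome. A subject who receives Dose 1, has nothing to report and leaves at Day 57 counts the same as one followed for 26 months without an event.

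The SAP does not treat other missing data this way. Section 12.2.5 excludes doses without symptom sheets from the solicited analysis, and Section 12.2.4 leaves missing titers unreplaced. Only for unsolicited events does missing observation become no event.

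Safety is a primary objective. Section 6.3 presents results by study group and pooled by adjuvant, and Section 7 aims to characterize differences in reactogenicity between groups. If withdrawal differs in amount or timing, the group that loses more subjects, or loses them earlier, looks safer than it is. An exact binomial interval does not reflect this.

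**Working it through.** **Inputs from the SAP.** Optimal intervals (Section 2): Visit 1 to Visit 4, 56 days; Visit 4 to Visit 8, 336 days; Visit 8 to Visit 12, 336 days. Total 56 + 336 + 336 = 728 days, and 728 / 28 = 26, which agrees with Month 26. Group size is 47, so a pooled adjuvant group has 3 × 47 = 141.

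**Assumptions, not in the SAP.** A true 26-month risk p, the same in both groups; a constant hazard; withdrawal unrelated to event risk; a fraction d of the group withdrawing. The SAP states no event or withdrawal rate, so ranges are shown.

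**Case A: withdrawal spread evenly over follow-up.** Let L = −ln(1 − p). A withdrawn subject has an event before leaving with probability 1 − (1 − e^(−L))/L = 1 − p/L. The expected tabulated percentage is

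(1 − d) × p + d × (1 − p/L).

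For p = 50%, L = 0.693 and 1 − 0.5/0.693 = 27.9%. With d = 5%: 0.95 × 50 + 0.05 × 27.9 = 48.9%. With d = 15%: 0.85 × 50 + 0.15 × 27.9 = 46.7%.

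| True risk | Tabulated, d = 5% | Tabulated, d = 15% | False gap (points) |
|---|---|---|---|
| 2% | 1.95% | 1.85% | 0.1 |
| 10% | 9.75% | 9.26% | 0.5 |
| 30% | 29.3% | 27.9% | 1.4 |
| 50% | 48.9% | 46.7% | 2.2 |

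At 5% versus 30% withdrawal, the gap is 1.2 points at 10% risk, 3.5 at 30% and 5.5 at 50%.

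**Case B: every withdrawal at Day 57.** The risk before leaving is 1 − (1 − p)^(56/728). For p = 50% this is 5.2%.

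- d = 5%: 0.95 × 50 + 0.05 × 5.2 = 47.8%.
- d = 20%: 0.80 × 50 + 0.20 × 5.2 = 41.0%.
- Gap: 6.7 points.

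For p = 30% the tabulated values are 28.6% and 24.5%, a gap of 4.1 points.

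**Equal withdrawal.** With the same d and the same timing in both groups the gap is zero, but each percentage is still too low. In Case A with d = 15% and p = 50%, both groups would show 46.7%.

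**Scale.** The exact 95% interval is 36.1 to 65.9% for 24/47 and 41.1 to 58.2% for 70/141, so about 30 and 17 points wide. The Case A gaps at 5% versus 15% are small beside these widths.

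**Whether the by-dose tables remove the problem.** Section 6.3 also presents safety by dose, so subjects who left before a dose are outside that dose's denominator. Section 12.2.2, however, assigns an event to the most recent dose. The Dose 2 and Dose 3 periods therefore last about 336 days each, again without an account of follow-up time. The overall-per-subject figures are unchanged.

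**The case against.** The strongest case on the other side is that this is a descriptive Phase I/II safety analysis in which differential loss would be visible. Withdrawal status and reasons are shown by group (Sections 6.1.1 and 6.1.2, Template 5), as are visit attendance (Template 7) and doses received (Template 13). Template 6 separates stopping treatment from leaving follow-up, so a subject who declines further vaccination is not necessarily lost to safety observation. The only adjuvant decision rule, in Section 7, uses ELISA GMT ratios, so no planned decision depends on these percentages. All of this stands. It limits the consequence, but visible withdrawal does not correct the percentages.

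Four stronger readings are tempting, and the SAP does not support them.

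- That every withdrawn subject counts as event-free. Only those with no report do; events reported before leaving, including any that caused the withdrawal, stay in the numerator.
- That pIMDs are affected in the same way. Section 6.3.1 and Template 21 plan a description and a listing, with no percentage.
- That the proportion of subjects is the only summary. SAEs also have event counts (Template 28) and a listing with onset day (Template 22). ILI has episode-based tables (Template 23) and a listing (Template 49).
- That a gap near 7 points should be expected. It requires high incidence, a fourfold difference in withdrawal and departure of all withdrawn subjects at Day 57; none of these is in the SAP.

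It is also fair to object that censoring is not neutral. If subjects leave because of a reactogenic dose, withdrawal may be related to event risk and a Kaplan-Meier estimate is then biased too. A single person-year rate is weaker still: with three vaccination visits and seasonal ILI the hazard is unlikely to be constant, and a group with early withdrawal contributes mostly time soon after a dose.

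**Conclusion.** The point holds for MAEs, SAEs and ILI over the whole study. Section 12.2.5 and Template 28 keep withdrawn subjects with no reported event in the denominator as event-free, and no planned output adjusts for the lost follow-up. The bias within a group is downward. Between groups it favours the one with more or earlier withdrawal, and it vanishes if amount and timing are equal.

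The size is an illustration, because the SAP gives no withdrawal rates. It is about 0.1 to 2 points for 5% versus 15% withdrawal spread over follow-up, and about 7 points in the worst case shown. Both rest on a constant hazard and on withdrawal unrelated to risk. For rare events such as SAEs the gap in points is small. The 28-day unsolicited tables are much less affected because the window is short. This is a cheap improvement to a descriptive analysis and does not invalidate the safety assessment.

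**What to change.** Keep the proportion tables, event counts and listings as planned. For MAE, SAE and ILI, add the Kaplan-Meier cumulative incidence of first event at Day 85, Month 14 and Month 26, by study group and pooled by adjuvant, with follow-up from Dose 1 and censoring at last contact. This needs no constant hazard.

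State in Section 12.2.5 that the no-report-means-no-event rule applies only to the 28-day windows and the proportion tables. Also state the assumption that censoring is unrelated to event risk. It is weaker than assuming that nobody has an event after leaving, but it is still an assumption. If person-year rates are added, make them supplementary and split them by post-dose period.

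The cost is a short SAP amendment and a few extra tables. Event onset is already derived (Section 12.2.1), and visit attendance and visit dates are already tabulated (Templates 7 and 8). The SAP does not name a last-contact date, so its derivation should be written down, for example as the latest attended visit or later documented contact.
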